---

## **The Clinical Impact of Stress CMR Perfusion Imaging in the United States (SPINS): A Global CMR Registry Substudy**

**Last approval date: October 29th, 2018**

### **Background**

Numerous single-center studies have indicated gadolinium-enhanced stress CMR perfusion imaging has excellent diagnostic accuracy for coronary artery disease and negative clinical event rates, with its diagnostic accuracy exceeding nuclear scintigraphy. However, current prognostic evidence supporting clinical use of stress CMR is limited by study size, single-center settings with a predominance of academic centers, and a lack of "real-world" study design. Large-scale multicenter real-world evidence from a registry will provide the much needed information to guide evidence-based clinical adaptation that benefits patient care.

The Global Cardiac Magnetic Resonance Registry (GCMR) registry effort by the Society for Cardiovascular Magnetic Resonance (SCMR) constitutes the only current global effort that includes multiple international CMR programs that span academic, community hospital, and private practice settings (<http://www.gcmr-scmr.org/>). This is also the only CMR registry that includes a large number of CMR sites in the United States. The GCMR is currently lead by [name] under the direction of the SCMR Executive Committee, the Chief Executive Officer, and the Board of Trustees. This leadership structure within the SCMR guarantees continuity and consistent quality for many years into the future. All of the data contributed by participating sites and the web database structure (<http://www.gcmr-scmr.org/>) are owned by the SCMR.

Based on a recent survey of the current 68,500 studies contributed from US-based CMR programs in the GCMR, there have been approximately 10,700 stress CMR perfusion studies performed since 2007. The US sites and their investigators that contributed these studies are listed in Table 1.

### Rationale and the Expected Deliverables of this Project

This proposal (Project 1) aims to assess the clinical impact of stress CMR perfusion guided treatments on patient outcomes in a 2,200 consecutive multicenter patient cohort, referred for assessment of myocardial ischemia in the United States. In the 3 specific aims presented below, we aim to obtain real-world evidence in patient outcomes including mortality and non-fatal cardiac outcomes, downstream cardiac procedures, invasive and non-invasive testing, costs in health care dollars based on national averages, and cardiac event-weighted quality adjusted life years (QALY). We believe these specific aims will provide the core evidence that medical insurance agencies and industries most sought after in making their reimbursement and payment decisions in the United States, towards the use of stress CMR perfusion imaging in patients with chest pain syndromes. At the end of the funding period, we expect multiple publications to result from each of the 3 specific aims which represent these core evidence.

### Study Cohort and Enrollment Criteria

Consecutive patients who underwent stress CMR perfusion imaging for evaluation of myocardial ischemia between 2008-2013.

**Inclusion Criteria:** all of the following at time of imaging:

- a) male or female at age 35-85 years,
- b) presence of either of the following sign/symptom that led to stress CMR imaging
  - 1) Symptoms suspicious of ischemia, or
  - 2) abnormal ECG with a suspicion of coronary artery disease
- c) Intermediate or high risk of significant coronary disease based on at least 2 of the following conditions:
  - a. patient age > 50 for male, 60 for female
  - b. Diabetes: by either history or medical treatment
  - c. Hypertension: by either history or medical treatment
  - d. Hypercholesterolemia: by either history or medical treatment
  - e. family history of premature coronary disease: first degree relative at age <= 55 male and <=65 female
  - f. Body mass index > 30
  - g. Any medical documentation of peripheral artery disease
  - h. Any history of myocardial infarction or percutaneous coronary intervention

**Exclusion Criteria:** any of the following at time of imaging:

- a) Prior history of coronary artery bypass surgery (CABG)
- b) Acute myocardial infarction within the past 30 days prior to CMR
- c) any significant non-coronary cardiac conditions confirmed by medical documentation
  - a. severe valvular heart disease,
  - b. non-ischemic cardiomyopathy with LVEF <40%,
  - c. infiltrative cardiomyopathy,
  - d. hypertrophic cardiomyopathy,
  - e. pericardial disease with significant constriction, or
- d) active pregnancy,
- e) any competing conditions leading to an expected survival of < 2 years
- f) Known inability to follow-up due to logistical reasons (e.g. patient lives in another country where follow-up is not feasible)

## Study Endpoints and Hypotheses to Test

### Study Endpoints

Primary outcomes include all-cause mortality, acute myocardial infarction (AMI), and late coronary revascularization (PCI or CABG beyond 60 days after CMR).

Secondary outcomes include non-fatal cardiac events (including cardiac hospitalizations for unstable angina or heart failure, heart transplant, significant ventricular arrhythmias, and strokes), alteration of diagnostic and therapeutic decision, and cardiac event-weighted QALY.

The specific aims of this project are listed below:

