### **Specific Aim 2 – Assessment of the impact of CMR-guided invasive coronary revascularization, compared with medical therapy, on primary outcomes**

Sub-aim 2.1 Using a propensity score-matching analysis, test the hypothesis that in real-world clinical practice that stress CMR perfusion imaging-guided use of invasive coronary revascularization (INT) (defined by INT performed within 60 days after CMR) offers *AMI-free, coronary revascularization-free, survival benefits* over medical therapy (MED) in patients with suspected ischemia. We will estimate the # lives saved per 100 patients treated with INT versus MED (based on predicted primary outcome rate amongst MED)–(predicted primary outcome rate amongst INT)

Sub-aim 2.2 Using a propensity score-matching analysis, test the hypothesis that in real-world clinical practice that stress CMR perfusion imaging-guided use of INT offers *survival benefits free of primary or secondary outcomes* over MED in patients with suspected ischemia.

Sub-aim 2.3 The preferred initial treatment for patients with stable ischemic heart disease (SIHD) is the best available medical therapy. The benefits of using physiologic ischemia-based guidance to performing INT has been shown in the FAME and FAME-2 trials where fraction-flow-reserve was used to assess physiological significance of coronary stenosis. In FAME (multi-vessel SIHD) and FAME 2 (single or multi-vessel SIHD) trials: a 29% and 66% relative risk reduction of primary outcome at 2-years were reported, respectively. CMR perfusion assessment had demonstrated remarkable correlation to FFR based assessment of coronary physiologic significance. For sub-aim 2.3, test the hypothesis that comparing to the FAME-2 primary outcome rate of patients managed by medical management alone, CMR-guided INT patients have a relative risk reduction of 2-year primary outcomes  $\geq 30\%$ .

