### **Specific aim 2 (2 separate analyses for sub-aims 2.1 and 2.2, respectively)**

We structured the present study's analysis of observational data to mimic a randomized clinical trial: a patient's assignment to a treatment was based on the therapy selected in the first 60 days after stress CMR perfusion study and nonrandomized treatment adjusted for via a propensity score. This time point of 60 days was selected from previous work indicating that revascularization performed within this timeframe resulted from the noninvasive imaging study, whereas referrals after 60 days tended to be attributable to worsening clinical status. Based on our pilot data, approximately 10-15% of patients undergo early coronary revascularization within the first 60 days after CMR. We therefore anticipate that 85-90% of the study cohort received MED whereas 10-15% received INT.

We plan to examine the assumptions of proportional hazards in each of the Cox models. In addition, performance of the propensity score model will be tested by comparing the prognostic associations between treatment and clinical outcomes, without and with that propensity score matching. Key risk markers will be compared between the treatment groups, without and with inclusion of the propensity score matching.

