**Step 1: Propensity Score to Treatment** We plan to structure the study analysis of observational data in SA1 to mimic a randomized clinical trial: a) assignment of coronary intervention (INT) vs. medical therapy (MED) is based on the therapy selected in the initial 60 days after imaging and b) nonrandomized treatment adjusted for via a propensity score. Either PCI or CABG will define coronary revascularization. Follow-up time begins at the time of the index stress CMR imaging. To adjust for non-randomization of treatment, a single propensity score will be developed using logistic regression to model the decision to refer to revascularization considering all factors known to influence the referral decision. This single composite propensity score represents the probability of treatment assignment, which will be included in all subsequent survival models (step 2) associating stress CMR perfusion guided-treatment with the respective endpoints in each of the 3 sub-aims. This adjustment reduces the bias introduced by nonrandomized referral to INT in practice. While all factors known to influence this referral decision will be considered for entry into this logistic regression model, based on existing literature, the most likely predictors of referral to INT include % ischemic myocardium (% myocardial mass based on number of segments, by CMR), typical angina symptoms (yes if positive response to 2 of 3 Diamond and Forrester qualities, else no), infarct size (LGE size, grams of myocardial mass), ischemic ST changes on rest ECG (yes/no), pre-test coronary disease probability (ordinal), and prior cardiac catheterization (yes/no). We anticipate that 10-15% of patients (~n=300) received INT so model over-fitting will not occur when constructing this logistic regression model.

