**Step 2: Multivariable survival analyses for treatment's impact incorporating the propensity score (sub-aims 2.1 and 2.2).** A Cox proportional hazards model will be used to assess the association of treatment with the primary outcome (sub-aim 2.1) and secondary outcome-free survival (sub-aim 2.2). For each of sub-aim 2.1 and 2.2, we plan to build a survival model using Cox proportional hazards regression to control for the effects of baseline patient differences. Key known risk markers to be included in these models are age, sex, diabetes, and % ischemic myocardium. Major Treatment (INT or MED) and the propensity score will then be entered into the model to assess for any survival advantage from INT vs MED adjusting for the nonrandomized referral pattern. Any potential impact by any covariate in the model onto the survival benefit from INT, will be tested by adding an interaction term between treatment and the covariate of interest.

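### Late revascularization in the sub-aim 2.1 composite counts a first procedure in MED but only a further one in INT, so INT can win, and be credited with lives saved, without any effect on death or MI

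*Combined protocol and SAP*

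**What the plan says.** All references are to the combined protocol and SAP.

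- *Study Endpoints*: besides all-cause death and acute MI, the primary outcome includes "late coronary revascularization (PCI or CABG beyond 60 days after CMR". *Clinical Outcomes within 4 years after CMR* repeats this.
- *Specific Aim 2*, sub-aim 2.1: the INT group is "defined by INT performed within 60 days after CMR", and the hypothesis concerns "AMI-free, coronary revascularization-free, survival benefits".
- *Statistical Analyses, Specific aim 2*, Step 1: "assignment of coronary intervention (INT) vs. medical therapy (MED) is based on the therapy selected in the initial 60 days after imaging". Follow-up starts at the index CMR.
- The same section, Step 2: "A Cox proportional hazards model will be used to assess the association of treatment with the primary outcome (sub-aim 2.1"), with the propensity score and baseline covariates in the model.
- Sub-aim 2.1 also states an effect measure: "We will estimate the # lives saved per 100 patients treated with INT versus MED (based on predicted primary outcome rate amongst MED"), minus the corresponding rate in INT.
- The reason given for the cut-off is that "referrals after 60 days tended to be attributable to worsening clinical status".

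No INT-versus-MED analysis of death or MI, or of death alone, is planned. Sub-aim 2.2 widens the composite by adding the secondary outcomes. Sub-aim 2.3 compares INT with a historical group.

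**The concern.** The same procedure is the treatment up to day 60 and a failure afterwards. For MED, the late-revascularization component mostly records that a patient eventually received the comparator treatment. For INT, it records repeat procedures. These are different events with different rates, and the clinicians who decide on them know the CMR result. The propensity score addresses baseline differences between the groups. It cannot make an endpoint component mean the same thing in both.

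What is at stake is the reading of the result. A difference made up wholly of later procedures in MED would satisfy the sub-aim 2.1 hypothesis and would then be converted into lives saved. The *Rationale and the Expected Deliverables* section says that the results are meant to inform reimbursement and payment decisions, so that number would travel without its definition.

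**Working it through.** **The plan's own figure.** *Sample Size* gives a detectable hazard ratio (HR) of 0.59 at 80% power, two-sided 5%, with a 77%/23% split and events counted as death and MI only. By Schoenfeld's formula, HR = exp[−(1.960 + 0.842)/√(D × 0.77 × 0.23)]:

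- D = 160 (the plan's 124 + 36): √28.34 = 5.32, so HR = 0.59. The figure reproduces.
- D = 150 (the total the plan lists): HR = 0.58.

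This power statement does not count late revascularization at all.

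**Inputs for the check.**

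- Death/MI rates from *Sample Size*: 0.5%/yr without ischemia, 6%/yr with ischemia, prevalence of ischemia 23%. Blended: 0.23 × 6% + 0.77 × 0.5% = 1.765%/yr.
- INT share from *Statistical Analyses, Specific aim 2*: 10–15%.
- Horizon: 4 years, the planned follow-up. The plan gives no horizon for lives saved.
- Assumed, because the plan has no figure: late first revascularization in MED (r_MED) and late repeat revascularization in INT (r_INT). Also assumed: one death/MI rate h for both groups, so the true death/MI HR is 1.

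**Formulas.** With constant rates:

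- Composite HR = (h + r_INT)/(h + r_MED).
- Lives saved per 100, as the plan would compute it = 100 × [exp(−4(h + r_INT)) − exp(−4(h + r_MED))].

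Worked case, h = 1.765%, r_MED = 3%, r_INT = 1%: HR = 2.765/4.765 = 0.58. The 4-year risks are 1 − exp(−0.1906) = 17.4% in MED and 1 − exp(−0.1106) = 10.5% in INT, a difference of 6.9 per 100.

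| h (%/yr) | r_MED (%/yr) | r_INT (%/yr) | Composite HR | Apparent lives saved per 100 |
|---|---|---|---|---|
| 1.765 | 2 | 1 | 0.73 | 3.5 |
| 1.765 | 3 | 1 | 0.58 | 6.9 |
| 1.765 | 2 | 2 | 1.00 | 0 |
| 1.765 | 1 | 2 | 1.36 | −3.5 |
| 6 | 3 | 1 | 0.78 | 5.8 |
| 6 | 4 | 1 | 0.70 | 8.5 |

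The 6%/yr rows show the case in which every patient has ischemia. At the blended rate with r_INT = 1%, the plan's detectable HR of 0.59 arises with no death/MI effect when r_MED = 2.765%/0.59 − 1.765% = 2.9%/yr.

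**Simulation check.** This used 300 Cox analyses with 12.5% INT, the worked-case rates and no revascularization event before day 60. The composite HR was 0.58, significant in favour of INT in 81% of runs. The death/MI HR was 0.98, significant in favour of INT in under 1%.

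**Precision of a death/MI analysis.** Expected events: 2,200 × [1 − exp(−4 × 0.01765)] = 150. The same Schoenfeld formula gives a detectable HR of 0.47, 0.50 and 0.53 for 10%, 12.5% and 15% INT. Power at HR 0.59 is 49%, 57% and 64%. These are approximate and probably optimistic for a small group with few events: in the worked case the formula gives 93% power at 12.5% INT, against 81% by simulation.

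**The case against.** The 60-day cut is a declared and reasoned choice. The plan cites previous work for it and says that later referrals tend to reflect worsening. Sub-aim 2.1 names its endpoint openly as revascularization-free. Any cut-point misclassifies some patients, and a planned second-stage procedure shortly after day 60 counts against INT, so error at the boundary runs both ways. All of this stands. It makes late revascularization a defensible component, but it does not make a first procedure in MED equivalent to a further one in INT, and it does not justify calling composite events lives.

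Three stronger readings are tempting, and the documents support none of them.

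- *The design is bound to favour INT.* The plan gives no late-revascularization rate for either group. The advantage needs the MED rate to exceed the INT repeat rate.
- *The spurious reduction is 14–33%.* A reader might take the 5%/yr in *Sample Size* as death/MI in both groups, with late rates of 2–4% in MED and 1–2% in INT. That gives 6/7 = 0.86, 7/9 = 0.78 and 6/9 = 0.67. But the same ranges include 2% against 2%, which gives 7/7 = 1.00, so the span is 0–33%. The plan also does not say that its 5%/yr is a death/MI rate.
- *The primary endpoint must be redefined, for example to procedures linked to an MI or unstable-angina admission.* That would keep the first-versus-further asymmetry, drop procedures for worsening angina without admission, and add little for MI, which is already an event. It would also give Aim 1 and sub-aim 2.1 different primary endpoints, in a document last approved in October 2018 for a project ending on 11/30/2018.

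**Conclusion.** The point holds as a possibility that the plan leaves open. It follows from the definitions alone that the sub-aim 2.1 composite can favour INT with no effect on death or MI. Neither the propensity score nor sub-aim 2.2 would reveal this. Labelling the composite difference as lives saved is wrong on the plan's own definitions and needs no assumed rate to show it.

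The size is conditional. At the blended death/MI rate, 3%/yr against 1%/yr is enough to produce an HR of 0.58, about the effect that the plan calls detectable. That rests on assumed late rates, constant hazards and a common death/MI rate. Other plausible rates give a smaller distortion, none, or one against INT.

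**What to change.** Keep the current composite for sub-aim 2.1 and add the following to the SAP before the Aim 2 analysis is run. If outcomes by group have already been seen, say so.

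1. An INT-versus-MED Cox analysis of all-cause death or acute MI, and one of all-cause death alone, with the same propensity adjustment and covariates.
2. Death, acute MI and late revascularization reported separately by group, with numbers and rates. The event times are already collected (*Clinical Outcomes within 4 years after CMR*; Appendix A4).
3. A survival-benefit statement only if the death/MI result points the same way as the composite, with its confidence interval shown beside it. The added analysis limits the claim and is not a second route to significance.
4. Lives saved computed from predicted all-cause mortality in each group, or the measure renamed as primary events avoided. In either case, state the time horizon.

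The cost is SAP text and a few extra models on existing data. No new data are needed and Aim 1 is unchanged. The real downside is precision. The death/MI analysis has fewer events and a wider interval, and with the detectable HRs shown above it may well be inconclusive. The SAP should say so in advance, so that a non-significant death/MI result is not read as evidence of no effect.

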### Specific Aim 1 – Association of CMR ischemic burden with clinical outcomes in the real-world

To test the hypothesis that stress CMR perfusion imaging adds predictive stratification of clinical outcomes over known risk factors for patients presenting with chest pain syndromes, at moderate pre-test risk, in a multicenter real-world setting in the US. Endpoints of interests include both primary and secondary outcomes. This aim is important because it provides the prognostic association of key CMR variables of ischemia with the observed primary and secondary events without and with adjustments to known clinical markers of patient risks, annualized event rates of primary and secondary outcomes either annualized across the entire study period or at specific intervals of study follow-up (e.g. first, second, third year of follow-up etc), net reclassification index by CMR metrics of ischemia towards current guideline-supported treatments, and potential alteration of diagnostic and therapeutic thinking.

Specific aim 1 will assess the prognostic association of presence of ischemia and percent ischemic myocardium (both by CMR) with the primary and secondary clinical outcomes. In the multi-variable analyses, key known risk markers such as patient age, patient sex, left ventricular and systolic volume (LVESV), validated pretest coronary disease probability, and validated risk score (Diamond and Forrester) will be considered for inclusion in a multivariable model, and then presence or extent of ischemia by stress CMR will be added to the model to test the null hypothesis that CMR assessment of ischemia do not add prognostic value, versus the alternative hypothesis that stress CMR assessment of ischemia do add predictive value. A significance level of 0.05 will be used. Since CMR findings will affect patient management, which in turn, will affect the clinical outcomes, in a secondary analysis, cardiac treatment (e.g. revascularization) received within 60 days of the CMR will be added to the above model to account for treatment effects on the relationship between extent of ischemia and outcome. Annualized event rates of the primary and secondary outcomes, stratified by CMR ischemia (present or absent), and CMR ischemic burden (mild, moderate, high), will be determined, both unadjusted and adjusted for cardiac treatments received. We also plan to calculate net reclassification index of these CMR metrics to event-free survival (primary and secondary outcomes).

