## Sample Size

### For sub-aim 1:

The rate of cardiac hard events (death and acute MI) is estimated based on reported evidence of 0.5% and 6% per year for patients who have absence and presence of ischemia on CMR perfusion imaging, respectively. We plan to collect follow-up events for a 4-year period after CMR. Based on prior evidence, prevalence of ischemia on CMR perfusion was 23% in referred patients.

With a sample size of 2,200 patients, 506 (23%) are assumed to be with presence of ischemia and 1694 (77%) with absence of ischemia. With incidences of 6% and 0.5% per year and a 4-year follow-up, a total of 124 of 506 patients with ischemia and 36 of 1694 patients with no ischemia are expected to experience an event, i.e. a total of 150 patients with event.

A sample size of 2,200 patients overall and 150 patients with event in a 4-year follow-up is regarded sufficient to run multivariable analysis with up to 10 variables.

With regards to the sample size considerations on the time-to-event analysis, the following settings and assumptions were used:

- Power = 80%
- Level of significance (two-sided) = 5%
- Assumed proportion in control group (i.e. no revascularization) = 77%
- Total sample size = 2,200 patients
- Number of events = 150 in total sample
- 4-year follow-up for all patients available
- The hazard ratio is estimated by a Cox proportional hazard model

With a sample size of 2,200 patients and an event rate of 124 in group 1 and 36 in group 2, a hazard ratio of 0.59 can be detected with the above mentioned settings and assumptions (i.e. 41% risk reduction rate).

For sub-aim 2.3 (comparison to the historical FAME 2 study

As reported in published data (own BWH dataset and [name] et al Circulation 2011 Apr 12;123(14):1509-18), the event rate of patients who underwent revascularization guided by CMR ischemia (i.e. CMR physiologic guidance) is about 5% per year, i.e. 10% in a 2-year follow-up. In the

historic fame-2 study, the 2-year event rate of patients who did not use physiological guidance (N=441), was 19.5%. With a power of 80%, a two-sided alpha of 5% and an assumed difference under H1 of -9.5%, the sample size of patients in this registry needs to be at least 180 patients.

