## **Statistical Analyses**

### **Specific aim 1**

Unadjusted and multivariable survival analyses associating presence of ischemia and percent ischemic myocardium (both by CMR), with the primary and secondary clinical outcomes will be performed. In the multi-variable analyses, key known risk markers such as age, patient sex, left ventricular and systolic volume (LVESV), validated pretest coronary disease probability, and validated risk score (Diamond and Forrester) will be modeled, and then extent of ischemia by stress CMR studies will be added to the model to test the null hypothesis that CMR findings do not add predictive value, versus the alternative hypothesis that stress CMR findings do add predictive value. A significance level of 0.05 will be used. Since CMR findings will affect patient management, which in turn, will affect the clinical outcomes, in a secondary analysis, cardiac treatment (e.g. revascularization) received within 60 days of the CMR will be added to the above model to account for treatment effects on the relationship between extent of ischemia and outcome. Annualized event rates of the primary and secondary outcomes, stratified by CMR ischemia (present or absent), and CMR ischemic burden (mild, moderate, high), will be determined, both unadjusted and adjusted for cardiac treatments received. We also plan to calculate net reclassification index of these CMR metrics to event-free survival (primary and secondary outcomes). In addition, we will examine the annual event rates of primary and secondary outcomes in each of these subgroups and perform corresponding comparative analyses.

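### Aim 1 tests one null hypothesis at 0.05 but does not fix which ischemia marker and which outcome decide it, so 5% holds only if a single test counts

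*Combined protocol and SAP*

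**What the plan says.** The added-value test is described twice in the combined protocol and SAP, with different markers.

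- **Specific Aim 1:** after the clinical risk markers are modeled, "then presence or extent of ischemia by stress CMR will be added to the model to test the null hypothesis".
- **Statistical Analyses, Specific aim 1:** the same step reads "then extent of ischemia by stress CMR studies will be added to the model to test the null hypothesis".

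On outcomes, the aim states "Endpoints of interests include both primary and secondary outcomes" and plans to relate "presence of ischemia and percent ischemic myocardium (both by CMR) with the primary and secondary clinical outcomes". The Statistical Analyses section repeats that plan for both markers and both sets of outcomes, and adds that "we will examine the annual event rates of primary and secondary outcomes in each of these subgroups and perform corresponding comparative analyses".

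On error control, the aim says "A significance level of 0.05 will be used". That the test is two-sided appears only in the sample-size section ("Level of significance (two-sided) = 5" percent). No section ranks the tests, divides alpha or marks any of these analyses as exploratory.

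Study Endpoints gives the primary outcomes as a list: "Primary outcomes include all-cause mortality, acute myocardial infarction (AMI), and late coronary revascularization". It does not say that Aim 1 analyzes them as one composite.

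**The concern.** There is one null hypothesis and one level, but several tests could be used to reject that null. Presence and extent can disagree, and so can the primary and secondary outcomes. If a significant result on any of them were reported as showing that stress CMR adds prognostic value, that conclusion would carry more than the stated 5% risk of being false.

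The risk is greater in a retrospective registry. The scans date from years before the plan's last approval in October 2018, so naming the test in advance is the main safeguard against choosing it once results are known. The Potential Impact section also expects the findings to support stress CMR as standard of care.

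**Working it through.** **1. The plan's own figure.** The sample-size text for sub-aim 1 gives a detectable hazard ratio of 0.59 at 80% power, two-sided 5%, with a 77%/23% split. By Schoenfeld's formula:

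events = (1.960 + 0.842)² / [0.77 × 0.23 × (ln 0.59)²] = 7.849 / (0.1771 × 0.2784) = 159.2, rounded up to 160.

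This matches the group counts, 124 + 36 = 160. The listed total of 150 would give a hazard ratio of 0.581, or 77.6% power at 0.59. The calculation is for one comparison at the full 5%, so it makes no allowance for several tests.

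**2. Number of tests.** Two markers by two outcome sets gives four, if each set is analyzed as one composite. Narrower readings give two (both markers on the primary outcome, or extent on both sets) or one (extent on a primary composite).

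**3. Independent tests at 0.05.**
- Two: 1 − 0.95² = 9.75%
- Four: 1 − 0.95⁴ = 18.5%

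**4. Correlation between markers (assumed).** Score extent as zero without ischemia, and let CV be the coefficient of variation of segment count among ischemic patients. At the plan's 23% prevalence, the correlation of presence with extent is 1/√(1 + CV²/0.77). The documents give no CV. A CV of 0.4 gives 0.91; a CV of 1.0 gives 0.66.

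**5. Correlated tests.** The chance of at least one |z| > 1.96 under the null, from 1,000,000 draws of four correlated normal statistics (all correlations assumed):

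| Qualifying tests | Marker correlation | Outcome correlation | False-positive rate |
|---|---|---|---|
| Extent on a primary composite | – | – | 5% |
| Both markers, primary only | 0.6-0.9 | – | 7.0-8.7% |
| Extent only, both outcome sets | – | 0-0.7 | 8.3-9.7% |
| Four | 0.9 | 0.9 | 9.8% |
| Four | 0.7-0.8 | 0-0.3 | 14.6-15.9% |
| Four | 0 | 0 | 18.5% |

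**6. Patient-level check.** Null cohorts of 2,200 were simulated with 23% ischemia, three assumed segment-count distributions, an assumed underlying event probability of about 7% for each outcome set, and 5,000 runs per setting. The tests were unadjusted for covariates.
- Four tests, separate outcome sets: 13.7-15.9%
- Four tests, secondary endpoint also containing the primary events: 12.0-13.8%
- Both markers on the primary outcome: 6.9-8.7%
- Extent on both outcome sets: 8.3-9.8%
- Extent on the primary outcome alone: 4.7-5.3%, as it should be

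**7. After correction.** One named test has a 5% error rate. Bonferroni over four tests (0.05/4 = 0.0125 each) keeps it at or below 5%; it is about 4.0% at marker correlation 0.8 and outcome correlation 0.3.

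**The case against.** The strongest defense is that the outcomes are already labelled primary and secondary, and the usual reading is that the primary outcome decides. If the Statistical Analyses section also governs the choice of marker, one test remains, at 5%. That reading is reasonable, but the plan does not state it. The labels do not choose between presence and extent, the two sections disagree on the marker, and the aim names both outcome sets for this hypothesis.

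A second defense is that the expected effect is large. At the plan's counts, the ratio of risks is (124/506)/(36/1694) = 11.5, and ln 11.5 / √(1/124 + 1/36) is about 13, far beyond any multiplicity-adjusted cut-off. This stands as a limit on the practical consequence: the inflation matters only if ischemia adds nothing. But these are unadjusted rates of death and AMI, and Aim 1 asks what ischemia adds after adjustment.

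A reader might go further and infer that the true error rate is 14-16%, about three times the stated level. The documents do not support that. It requires four qualifying tests, a significant secondary outcome counting as success, and particular correlations; none of these is stated. Nor do they support the higher figure of about 25-27% that results from testing death, AMI, late revascularization and the secondary composite separately with both markers. No section plans that for Aim 1, and sub-aim 2.1 reads as a composite. The annual-rate comparisons should not be counted as further tests of this null either; they need a label, not a place in the tally.

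**Conclusion.** The concern holds as a failure to specify the deciding test. The two descriptions of the Aim 1 test name different markers, both outcome sets are in scope, and nothing orders or adjusts the tests. The stated 0.05 is then the error rate only if one marker on one primary composite decides. Otherwise it is about 7-10% with two qualifying tests and about 10-18.5% with four. These ranges rest on assumed correlations between markers and between outcomes, on each test being run at two-sided 0.05, and on ischemia truly adding nothing. No single figure within them can be attributed to the plan.

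The sample-size section does not settle which marker was intended. Its event projection contrasts presence with absence of ischemia, but it counts only death and AMI, and its hazard-ratio settings label the control group as not revascularized.

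**What to change.** Make Specific Aim 1 and the Statistical Analyses section name the same deciding test:

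- **Deciding test:** one ischemia marker, with its coding, chosen by the investigators and recorded before analysis. It is added to the stated multivariable model for the composite of death, AMI and late revascularization, at two-sided 0.05.
- **Other tests:** the other marker and the secondary composite in a stated fixed order, each at 0.05 and only if the previous test is significant; or label them supportive. State which events form the secondary composite, since Study Endpoints also lists decision changes and QALY as secondary outcomes.
- **Annual-rate and subgroup comparisons:** label as exploratory and report with confidence intervals.

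The cost is wording. No extra patients or data are needed, and the deciding test keeps the full 0.05. The small downside is that later results cannot be claimed as confirmatory if an earlier step fails.
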